7.3 REPORTING PROCEDURES

All adverse events will be reported. Depending on the nature of the event the reporting procedures below will be followed. A flowchart is given below to aid in the reporting procedures.

7.3.1 Non serious AR/AEs

All such toxicities, whether expected or not, will be recorded in the toxicity section of the relevant case report form and sent to the study coordination centre within one month of the form being due.

7.3.2 Serious AR/AEs

Fatal or life threatening SAEs and SUSARs will be reported on the day that the investigators are aware of the event. The SAE form asks for nature of event, date of onset, severity, corrective therapies given, outcome and causality (i.e. unrelated, unlikely, possible, probably, definitely). The responsible investigator ([name]) will sign the causality of the event. Additional information should be sent within 5 days if the reaction has not resolved at the time of reporting.

SAEs

[figure not shown]
An SAE form will be completed and faxed to the Imperial College Joint Research Compliance Office for review.

SUSARs

In the case of serious, unexpected and related adverse events, the staff involved in the study will:

- Or
 - Complete the SAE case report form & send it immediately (within 24 hours, preferably by fax), signed and dated to [name] together with relevant treatment forms and anonymised copies of all relevant investigations.
 - Contact the [name] by phone and then send the completed SAE form to [name] within the following 24 hours as above.

[name] will notify the MHRA, main REC and Sponsor of all SUSARs occurring during the study according to the following timelines; fatal and life-threatening within 7 days of notification and non-life threatening within 15 days. All investigators will be informed of all SUSARs occurring throughout the study.

* Unless identified in the protocol as not requiring immediate reporting

Contact details for reporting SAEs and SUSARs

[contact], attention [name]

Please send SAE forms to: [name]

[contact] (Mon to Fri 09.00 – 17.00)

8. ASSESSMENT AND FOLLOW-UP

Each participant will be in the study for the period of their IVF treatment, which will be no longer than eight weeks. Following this if the patient becomes pregnant they will have routine antenatal follow up for the duration of their pregnancy and delivery at Queen Charlottes' Hospital. There will be no additional interventions needed during the pregnancy related to the study but we will follow up patients until the birth of their child.

8.1 LOSS TO FOLLOW-UP

The patients who are lost to follow from this study will be contacted using their telephone and address details supplied at the time of entry into the study to ensure safety. As far as data analysis an intention to treat analysis will be carried out for this study and sensitivity analysis will be used in data analysis to take account of the small number of drop outs that may occur in the study.

8.2 TRIAL CLOSURE

The study will stop recruiting patients when the optimal dose of kisspeptin required to trigger oocyte maturation has been determined. The optimal dose of kisspeptin will be the dose of kisspeptin which causes oocyte maturation in >90% of women (n=15). However, we will continue to follow up all women in the study until they have completed their pregnancy.

9. STATISTICS AND DATA ANALYSIS

Sample size calculation: For the primary endpoint of oocyte maturation in the proposed patient population, there is no directly relevant data that has been published previously upon which sample sizes estimates could be based. However, there is evidence in the literature (13) of a relationship between successful oocyte maturation and rises in luteinising hormone (LH) which can be used as a basis for sample size calculations for this study. In that study, successful oocyte maturation occurs following a mean rise in LH of 106IU/L at 4hours following a GnRH agonist trigger in a FSH/GnRH antagonist IVF protocol. Our previous dose finding studies of kisspeptin on LH release in normal women in the preovulatory phase of their menstrual cycle show that kisspeptin (12.8nmol/kg) can increase LH by up to 148IU/L with an estimated SD of 78IU/L. Using the 2-group t-test approach, we have calculated that with 13 patients in for each dose of kisspeptin tested will have at least 90% power to detect a difference of 148IU/L amongst any 2 groups (2-sided 5% significance level without correction for multiplicity and common standard deviation of 78 IU/L) (nQuery Advisor Version 5.0. Statistical Solutions, Cork, Ireland). This n number is similar to that used in our recent studies of kisspeptin on LH release in normal women in the preovulatory phase of their menstrual cycle (n=8) to show a significant effect of kisspeptin on LH release compared to controls (8). It is anticipated that the drop-out rate will be less than 10% (based on similar previous studies in these highly motivated infertile patients). Therefore, fifteen women for each of the 6 doses of kisspeptin (0.4, 0.8, 1.6, 3.2, 6.4 and 12.8nmol/kg) administered will be recruited to allow for dropouts during the study and each woman will only participate in the study once. As such a total of 90 women will be recruited to the study.

Data analysis for the study:

The statistical data analysis will be carried out by Imperial Clinical Trials Unit under the supervision of [name] (Professor of Medical Statistics and Clinical Trials, Imperial College London). An intention to treat analysis will be carried out for this study and sensitivity analysis will be used in data analysis to take account of the small number of drop outs that may occur in the study. The primary analysis of the primary endpoint (oocyte maturation) will employ a logistic model to characterise the relationship between dose of kisspeptin and oocyte maturation. Additionally Bayesian analysis methods will be employed to characterise the relationship between dose of kisspeptin, LH and oocyte maturation.

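### The power statement uses 148 IU/L, an LH rise after the top dose, as a difference between any two dose groups, and 13 per group does not follow from it

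*Protocol*

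**What the plan says.** Protocol section 9 explains that no published data bear directly on oocyte maturation in this population, so the sample size is based on LH. It gives two LH figures:

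- From a cited study of a GnRH agonist trigger: "successful oocyte maturation occurs following a mean rise in LH of 106IU/L at 4hours".
- From the investigators' own dose-finding work in normal preovulatory women: 12.8 nmol/kg of kisspeptin "can increase LH by up to 148IU/L with an estimated SD of 78IU/L".

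The calculation is then described as "Using the 2-group t-test approach". With "13 patients in for each dose of kisspeptin tested", the study "will have at least 90% power to detect a difference of 148IU/L amongst any 2 groups", at a "2-sided 5% significance level without correction for multiplicity and common standard deviation of 78 IU/L". Allowing for dropout, 13 becomes 15 for each of six doses from 0.4 to 12.8 nmol/kg, 90 women in all.

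Section 5.1 says that every woman receives kisspeptin, so there is no untreated group. Under the data analysis heading of section 9, the primary analysis is a logistic model of oocyte maturation on dose, not a t-test on LH. Section 6.1 and the SAP describe a different comparison, one against two doses of kisspeptin, and the SAP plans 31 women per group.

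**The concern.** A two-group power calculation needs the expected difference between the two groups. The figure used is the rise produced by one dose, the highest of the six. It would be a between-group difference if the comparator did not raise LH at all, as an untreated control might not. The n=8 study cited in support did compare kisspeptin with controls, but this design has no such arm.

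The stated n is a second sign that something is amiss. A standardised difference of 148/78 = 1.90 is very large, and 13 per group is more than it needs.

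Neither document contains any other power calculation. A funder, ethics committee or data monitoring committee that relies on this sentence could think the trial better able to separate dose groups on LH than it is.

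**Working it through.** **Inputs, all from Protocol section 9.** SD 78 IU/L; two-sided 5% test, no multiplicity correction; 13 evaluable women per dose; difference 148 IU/L; the other LH figure in the paragraph, 106 IU/L.

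**Method.** Two-sample t-test with n per group and df = 2n − 2. The noncentrality parameter is λ = δ / (SD × √(2/n)). Power is the probability that a noncentral t with that df and λ exceeds the 5% critical value; the opposite tail is negligible for large λ.

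**Step 1: the plan's own figure.** For n = 13, SD × √(2/13) = 78 × 0.392 = 30.59, df = 24 and the critical value is 2.064. With δ = 148, λ = 148/30.59 = 4.84 and power is 99.6%. So at least 90% is true, but 90% is not what these inputs give.

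**Step 2: the n that 148 requires.** For n = 7, SD × √(2/7) = 41.69, df = 12, critical value 2.179, λ = 148/41.69 = 3.55, power 90.2%. For n = 6, power is 84.1%. The answer is 7 per group, not 13.

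**Step 3: what would give 13.**
- δ = 106: λ = 106/30.59 = 3.46, power 91.4% at n = 13 and 88.9% at n = 12. This gives exactly 13.
- δ = 148 with Bonferroni correction over all 15 dose pairs (α = 0.05/15 = 0.0033): power 92.8% at n = 13 and 89.4% at n = 12. This also gives 13, but the protocol says that no correction was made.

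**Step 4: the difference that 13 per group detects.** Power is 90% at λ = 3.38, so δ = 3.38 × 30.59 ≈ 103 IU/L.

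**Step 5: can two dose groups differ by 148?** Suppose mean rises lie between 0 and 148 IU/L. A gap of 148 then requires one group at the maximum and the other at zero. It cannot hold for every pair: three groups within that range cannot all be 148 apart. If the mean rise also never falls as dose increases, the five gaps between adjacent doses sum to at most 148 and average at most 148/5 = 29.6 IU/L.

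**Step 6: power at other differences, n = 13, SD 78.** The documents give no LH rise for any planned dose below 12.8 nmol/kg, so the last two rows are illustrations.

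| Difference (IU/L) | λ | Power |
|---|---|---|
| 148 (as stated) | 4.84 | 99.6% |
| 106 (rise after GnRH agonist) | 3.46 | 91.4% |
| 103 | 3.38 | 90% |
| 74 (half of 148) | 2.42 | 64% |
| 29.6 (one of five equal steps to 148) | 0.97 | 15% |

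**Step 7: dropout.** 13/(1 − 0.10) = 14.4, rounded up to 15, and 6 × 15 = 90. Both figures reproduce.

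**The case against.** The strongest reply is that the sentence is not false. It is conditional: if two groups differ by 148 IU/L, power is at least 90%. With equal group sizes and a common SD, that holds whichever pair is compared. It does not predict that every pair will differ by 148, and an n above the minimum is no error. This stands. A reader might infer that the protocol promises 90% power between any two doses whatever their difference; it does not. What remains is that the difference chosen is one the design could produce at most for an extreme contrast (a top dose at the maximum against an inert low dose), and that n = 13 does not come from it.

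A second reply is that no decision rests on pairwise LH tests. Section 8.2 defines the optimal dose by the proportion of women with oocyte maturation, section 6.1 by the highest level of maturation, and the primary analysis is a logistic dose-response model. This also stands. It would be tempting to conclude that dose selection is underpowered because adjacent doses have only 15% power on LH. The documents do not support that: they plan no such test, and the 15% rests on an assumed spacing of the dose response.

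A third inference to avoid is that 148 was typed in place of 106. The match with 13 is exact, but the documents do not record the derivation, and the Bonferroni route gives the same n.

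Finally, section 6.1 and the SAP describe a one-versus-two-dose trial, so the six-dose calculation may no longer govern. It is still current text in section 9 and is the justification given for 90 women.

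**Conclusion.** The point holds as a mis-specified effect size and a sample size that does not follow from it. The difference of 148 IU/L is a full rise after the top dose. It needs 7 per group rather than 13, and the 13 per group stated give 90% power only from about 103 IU/L upwards. These figures use only the protocol's SD, test and significance level.

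Two statements rest on assumptions. That a gap of 148 requires a non-responding group assumes mean rises between 0 and 148 IU/L. The powers at 74 and 29.6 IU/L are illustrative. If the reported maximum is a group mean rather than an individual value, the conclusion is the same, because it is still a rise after one dose.

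The consequence is limited. The power justification is misleading as written, but the calculation says nothing either way about the power of the logistic analysis of oocyte maturation or of the SAP's comparison of one with two doses.

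**What to change.** In Protocol section 9:

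1. Replace the power sentence with: 13 evaluable women per dose give 90% power to detect an LH difference of about 103 IU/L between two dose groups (SD 78 IU/L, two-sided 5%, no multiplicity correction). Remove 148 IU/L as the difference for any two groups.
2. State that 148 and 106 IU/L are full rises after a trigger, not differences between doses. Putting 106 in place of 148 would leave the same weakness.
3. State that power is lower for smaller between-dose differences, with 64% at 74 and 15% at 29.6 IU/L marked as illustrations.
4. State that the LH calculation does not give the power of the logistic analysis of oocyte maturation or of the one-versus-two-dose comparison in section 6.1 and the SAP.
5. Record how 13 was obtained, if the original calculation can be found.

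The figure of 103 IU/L is solved back from n. It describes what the design can detect and does not show that such a difference is plausible or relevant. The cost is a protocol wording change and a less favourable stated power; no added patients are needed.

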10. MONITORING

10.1 RISK ASSESSMENT

A risk assessment will be carried out according to the sponsor's standard operating procedures (SOPs).

10.2 MONITORING AT LOCAL SITE

Imperial College will risk assess the project and monitoring will be carried out according to the sponsors SOPs.

11. REGULATORY ISSUES

11.1 CLINICAL TRIALS AUTHORISATION (CTA)

A Clinical Trials Authorisation from the UK Competent Authority will be obtained.

11.2 ETHICS APPROVAL

The Study Coordination Centre has submitted an ethics application to the Hammersmith and Queen Charlotte's Research Ethics Committee. The study will be conducted in accordance with the recommendations for physicians involved in research on human subjects adopted by the 18th World Medical Assembly, Helsinki 1964 and later revisions.

11.3 CONSENT

Consent to enter the study will be sought from each participant only after a full explanation has been given, an information leaflet offered and time allowed for consideration. Signed participant consent will be obtained. The right of the participant to refuse to participate without giving reasons will be respected. After the participant has entered the trial the clinician remains free to give alternative treatment to that

specified in the protocol at any stage if he/she feels it is in the participant's best interest, but the reasons for doing so will be recorded. In these cases the participants remain within the study for the purposes of follow-up and data analysis. All participants are free to withdraw at any time from the protocol treatment without giving reasons and without prejudicing further treatment.

11.4 CONFIDENTIALITY

Participants' identification data will be required for the registration process. The Study Coordination Centre will preserve the confidentiality of participants taking part in the study and is registered under the Data Protection Act.

11.5 INDEMNITY

Imperial College holds Public Liability ("negligent harm") and Clinical Trial ("non-negligent harm") insurance policies which apply to this trial.

11.6 SPONSOR

Imperial College London will act as the main sponsor for this study. Delegated responsibilities will be assigned to the NHS trusts taking part in this study.

11.7 FUNDING

An MRC Developmental Clinical Studies grant application has been submitted to fund this study (outcome July 2010). This is an academic study and the investigators will not be paid for recruiting patients into this study.

11.8 AUDITS AND INSPECTIONS

The study may be subject to inspection and audit by Imperial College London under their remit as sponsor, the Study Coordination Centre and other regulatory bodies to ensure adherence to GCP.

12. TRIAL MANAGEMENT

A Trial Management Group (TMG) will be appointed and will be responsible for overseeing the progress of the trial. The day-to-day management of the trial will be co-ordinated by [name]. In addition a Data Monitoring Committee will be convened (for further details please see the Data Monitoring & Ethics Committee (DMEC) Standard Operating Procedure enclosed in with this application).

13. PUBLICATION POLICY

All publications and presentations relating to the study will be authorised by the Trial Management Group. The first publication of the trial results will be in the name of the Trial Management Group, if this does not conflict with the journal's policy. If there are named authors, these will include at least the trial's Chief Investigator, Statistician and Trial Coordinator. Members of the TMG and the Data Monitoring Committee will be listed and contributors will be cited by name if published in a journal where this does not conflict with the journal's policy.

APPENDIX 1. SUMMARY OF INVESTIGATIONS, TREATMENT AND ASSESSMENTS

All of the women in this study will undergo a standard FSH/GnRH antagonist IVF protocol with luteal phase supplementation which is used as part of routine care for women undergoing IVF treatment at Hammersmith Hospital (see appendix 2) under the supervision of [name] (Director of the IVF Unit). The only difference will be that women taking part in the study will have:

1. a single subcutaneous injection of kisspeptin in place of hCG in order to trigger oocyte maturation.
2. Plasma LH, FSH, progesterone and oestradiol will be measured immediately before kisspeptin injection and then after kisspeptin injection on up to 6 occasions during the first 24h and finally at the time of oocyte retrieval. These hormone measurements will determine the time course following kisspeptin injection at which an endogenous LH surge occurs which will be used to confirm the timing of oocyte retrieval.

All of the other procedures that the patients will have are part of routine care and would be the same for volunteers not participating in the study.

APPENDIX 2. STANDARD FSH/GNRH ANTAGONIST IVF PROTOCOL WITH LUTEAL PHASE SUPPLEMENTATION

All of the women in this study will undergo a standard FSH/GnRH antagonist IVF protocol with luteal phase supplementation which is used as part of routine care for women undergoing IVF treatment at Hammersmith Hospital (see appendix 2) under the supervision of [name] (Director of the IVF Unit). The current protocol is detailed below. This will be updated according to best clinical care.

Daily subcutaneous (sc) FSH injections (Gonal F) will be commenced on day 2 of the patient's menstrual cycle. Daily GnRH antagonist administration (Cetrotide) will be used to inhibit a premature

LH surge and will be started on the 5th day of FSH injections. The patient will attend 5 days after commencing the FSH injections for a pelvic ultrasound scan (USS) to determine ovarian follicular development. The patient will be asked to attend for further scans according to follicular size and response (if the largest follicle is 10-12mm the next USS will be 3 days later, if the largest follicle is 13-15mm the next USS will be 2 days later, if the largest follicle is 16mm daily USS will be performed). When 3 ovarian follicles of \geq 17mm have developed, the FSH and GnRH antagonist injections will be stopped. Kisspeptin will be given in place of hCG at this point in the protocol as detailed in section 6.1 of the protocol to cause oocyte maturation.

Thirty two to thirty six hours later, transvaginal ultrasound-directed oocyte retrieval will be carried out. Oocyte maturation will be determined using standard criteria (calculations of the percentage of metaphase II (MII) oocytes and fertilisation rate (number of two pronuclear (2PN) oocytes / number of metaphase oocytes injected) (15). ICSI will be carried out using fresh sperm from the male partner. The quality of the embryos will be classified as high quality (score 1), medium quality (score 2), and low quality (score 3) as previously described (30). One or two embryos of highest quality will be transferred to the uterine cavity of the patient on day 3-5 after oocyte collection. The remaining embryos will be frozen for the patient to use in future if required. Progesterone and oestradiol (at dosages recommended by the IVF team) will be started on the morning after oocyte collection until 12 weeks of pregnancy for luteal phase supplementation. After oocyte retrieval doxycycline (100mg bd) will be given for 7 days as well as analgesia as required (diclofenac suppository or paracetamol). Women will be followed up according to the standard protocol of the IVF Unit at Hammersmith Hospital. Women in whom kisspeptin does not result in oocyte maturation will receive a further IVF cycle (i.e. with hCG as a trigger for oocyte maturation) as part of their standard care. Pregnancy will be defined biochemically by a plasma β hCG concentration >10 iu/l 12 to 16 days after embryo transfer. Pregnancy will be defined clinically as an intrauterine gestational sac with a heartbeat 2-3 weeks after a positive hCG test. An additional ultrasound scan may also be performed at 7 weeks if there is clinical suspicion of an ectopic pregnancy. In women with a clinical pregnancy, standard pregnancy follow up will occur at Queen Charlotte's Hospital. Pregnancy outcomes and live births will be documented. IVF clinicians will make decisions in the best clinical interest of patients to safeguard patient safety where necessary as would occur in normal clinical practice.

APPENDIX 3. DETAILS OF THE IMP

The IMP is kisspeptin-54. Doses between 0.4 and 12.8nmol/kg will be administered during this study. The IMP has been manufactured and labelled in compliance with Good Manufacturing Practice Annex 13 by Bachem Switzerland. Please see the Investigators Brochure for further details of the IMP and for storage conditions.

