5.2 UNBLINDING

This is an open label, dose escalation, phase 2 clinical trial investigating the administration of Kisspeptin to induce oocyte maturation and all women will receive at least one dose of kisspeptin. Women will receive either one, or two doses of kisspeptin at least 8 hours apart. Women will be advised that the first injection will be kisspeptin for all women, but the second injection received may be either kisspeptin or saline.

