6. TREATMENTS

6.1 TREATMENT ARMS

All of the women in this study will undergo a standard FSH/GnRH antagonist IVF protocol with luteal phase supplementation which is used for women undergoing IVF treatment at Hammersmith Hospital under the supervision of [name] (Director of the IVF Unit) (please see appendix 2). The only difference will be that women taking part in the study will have either one or two subcutaneous injections of kisspeptin in place of hCG in order to trigger oocyte maturation. This injection will be administered by two experienced physicians at the Hammersmith Hospital or in the participant's home according to the patients preference.

The patients will be administered with the first dose of kisspeptin 12-24 hours after the last injection of FSH/GnRH antagonist for final oocyte maturation. Women will be randomised to receive either a single dose of kisspeptin (9.6nmol/kg), or two doses of kisspeptin 8-12 hours apart. The optimal dosing regimen of kisspeptin will be the dose of kisspeptin which causes the highest level of oocyte maturation.

Since kisspeptin causes a rapid and potent rise in LH release following sc injection we would expect that kisspeptin will induce oocyte maturation at a similar timing as when hCG or GnRH are used to trigger oocyte maturation which is 32-36 hours after injection (13, 16, 17, 18). In order to determine the changes in reproductive hormones which occur during oocyte maturation, participants will be given two options for blood testing following injection of kisspeptin. These options will be discussed at screening, and participants are entirely free to decline overnight blood sampling without altering their study participation or clinical care:

Option 1. Overnight blood sampling: Participants opting for overnight blood sampling will be admitted to the Wellcome / NIHR Clinical Research Facility (CRF), Hammersmith Hospital. Blood will be sampled for measurement of plasma LH, FSH, progesterone, kisspeptin and oestradiol. Total blood loss will not exceed 100ml, and blood sampling will not be performed more frequently than every 15min.

Option 2. Less intensive blood testing: In participants who do not opt into overnight blood sampling, plasma LH, FSH, progesterone and oestradiol will be measured immediately before kisspeptin injection, on up to six occasions within the first 24h following kisspeptin injection (according to participant availability), and then at the time of oocyte retrieval.

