**The use of the Hormone Kisspeptin in *in vitro* fertilisation (IVF) treatment.
Statistical Analysis Plan, version 3.0**

Date: 24/06/2015

MAIN SPONSOR: Imperial College London

FUNDERS: Medical Research Council (MRC)

STUDY COORDINATION CENTRE: Imperial College London

Protocol Code Number ICL/KISS/12/01

EudraCT number 2012-000154-61

Research Ethics Committee (REC) reference: 10/H0707/2

NCT No. NCT01667406

Statistical Analysis Plan, version 3.0

Date: 24/06/2015

Study: One versus 2 doses of kisspeptin (10hrs apart)

Participants will undergo controlled ovarian stimulation using a recombinant FSH/GnRH antagonist protocol and receive either one (Single) or two doses (Double) of kisspeptin-54 (9.6nmol/kg each dose) to trigger oocyte maturation.

On day 2 or 3 of the menstrual cycle, patients will receive daily SC recombinant FSH (recFSH) injections (Gonal F 112.5 IU, Merck Serono, Geneva, Switzerland, administered daily at midday); pelvic ultrasound scan will be performed five days after commencing recFSH, to determine ovarian follicular development. Daily subcutaneous GnRH antagonist injections (Cetrotide 0.25mg, Merck Serono, injected at 9pm daily) will be used to inhibit a premature LH surge, and will be commenced on day 5 of recombinant FSH injections. If serum LH is undetectable (<0.5 IU/L) on Day 7 of recombinant FSH injections, then the dose of cetrotide will be halved to 0.125mg daily. Further ultrasound scans will be performed according to follicular size and response to superovulation. When at least three ovarian follicles \geq 18mm diameter are visible on ultrasound, all patients will receive a subcutaneous bolus injection of kisspeptin-54 administered by a study investigator to trigger oocyte maturation at 36hrs prior to egg collection (between 2030 and 2300h). The dose of kisspeptin-54 will be weight-adjusted (9.6nmol/kg). Patients will then be randomized to receive either a second dose of kisspeptin (9.6nmol/kg), or saline placebo injection at 10hrs following the first kisspeptin trigger injection.

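### The protocol contradicts itself and the SAP on the kisspeptin regimen: Section 9 plans six doses that do not include 9.6 nmol/kg, while Section 6.1 and the SAP randomise women to 9.6 nmol/kg once or to two injections.

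*Protocol*

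**What the plan says.** The regimen is described in six places.

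- **Protocol Section 9** builds the sample size on "fifteen women for each of the 6 doses of kisspeptin (0.4, 0.8, 1.6, 3.2, 6.4 and 12.8nmol/kg) administered will be recruited". It gives a total of 90 and mentions no second injection.
- **Protocol Section 6.1** states: "Women will be randomised to receive either a single dose of kisspeptin (9.6nmol/kg), or two doses of kisspeptin 8-12 hours apart". It gives a size for the single dose and none for either of the two doses.
- **Protocol Section 5.2** agrees that there are one or two injections: "Women will receive either one, or two doses of kisspeptin at least 8 hours apart". It adds that the second injection may be saline.
- **SAP, opening study description**, has women "receive either one (Single) or two doses (Double) of kisspeptin-54 (9.6nmol/kg each dose) to trigger oocyte maturation". It then specifies "either a second dose of kisspeptin (9.6nmol/kg), or saline placebo injection at 10hrs following the first kisspeptin trigger injection". Later it expects 62 women, 31 per group.
- **Protocol Appendix 1** describes "a single subcutaneous injection of kisspeptin in place of hCG in order to trigger oocyte maturation". The Treatment entry of the Study Summary also refers to one injection.
- **Protocol Appendix 3** states: "Doses between 0.4 and 12.8nmol/kg will be administered during this study". It lists no dose levels, does not mention a second injection, and does not say whether the range applies to each injection or to each woman.

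Two further parts of the protocol depend on the dose plan. Section 9 makes the primary analysis a logistic model relating kisspeptin dose to oocyte maturation. Section 8.2 stops recruitment once a dose produces maturation in more than 90% of women, with n=15.

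**The concern.** A reader of Section 9 would run a six-level dose study. A reader of Section 6.1 or the SAP would run a two-arm randomised comparison at a dose Section 9 does not list. A reader of the Study Summary or Appendix 1 would give one injection to everyone. Nothing in the current text says that these are successive stages or that one supersedes another.

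Three things are at stake. First, the protocol alone does not define the treatment in one randomised arm, because the size of its injections is given only in the analysis plan. Second, the protocol's only sample size argument concerns dose groups that the SAP does not study. Third, the one statement of dose range in the protocol does not say how it applies to a woman who receives two injections, so anyone overseeing exposure has to guess its unit.

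**Working it through.** **1. The Section 9 total.** Inputs from Section 9: 13 women per dose, drop-out below 10%, six doses.

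- Inflation: 13 / (1 − 0.10) = 14.4, rounded up to 15.
- Total: 15 × 6 = 90, as stated.
- Power: for a difference of 148 IU/L, SD 78 IU/L, 13 per group and a two-sided 5% level, the two-sample t-test (noncentral t, 24 df) gives 99.6%. The claim of at least 90% is therefore true as worded.

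The Section 9 arithmetic is sound. The difficulty is which groups it describes.

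**2. The SAP total.** 31 × 2 = 62. The SAP gives this as an expectation, without a calculation. It is not a multiple of 15, and it does not follow from the Section 9 argument.

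**3. Does 9.6 nmol/kg appear in the Section 9 list?** The list is 0.4, 0.8, 1.6, 3.2, 6.4, 12.8. There is no match in six. The value falls between the two highest levels.

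**4. Number and size of injections, side by side.**

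| Place | Injections | Size of each (nmol/kg) | Women |
|---|---|---|---|
| Protocol Section 9 | no second injection described | six levels, 9.6 not included | 90 |
| Protocol Section 6.1 | one or two, 8–12 h apart | 9.6 if one; not stated if two | – |
| Protocol Section 5.2 | one or two, at least 8 h apart | not stated | – |
| SAP | one or two, 10 h apart | 9.6 each | 62 |
| Study Summary (Treatment entry), Appendix 1 | one | not stated | – |

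The three spacings are compatible with each other. The number of injections, the dose and the number of women are not.

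**5. The Appendix 3 range.**

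- Per injection: 0.4 ≤ 9.6 ≤ 12.8, so each injection is inside; 9.6 / 12.8 = 0.75.
- Per woman, using the SAP's injection size: 2 × 9.6 = 19.2; 19.2 − 12.8 = 6.4 above; 19.2 / 12.8 = 1.5.

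The figure of 19.2 cannot be derived from the protocol alone, because Section 6.1 gives no size for the two-dose arm.

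**6. What the Section 9 model would estimate under the SAP regimens.** If dose means injection size, it is 9.6 for every woman, and a slope on dose cannot be estimated. If dose means the total, it takes two values, 9.6 and 19.2. The slope is then the between-arm log odds ratio divided by 19.2 − 9.6 = 9.6, which is a two-group comparison and not a dose-response curve. The SAP plans an absolute difference between two groups.

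**7. The closure rule.** Section 8.2 is framed by dose, with 15 women. The SAP has 31 per arm and one injection size, so the rule has no defined application to it. Section 6.1 also defines the optimal regimen differently, as the one giving the highest maturation.

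**The case against.** The strongest reply is that the regimen is not really in doubt. The SAP is explicit, Sections 5.2 and 6.1 agree with it on one or two injections, and the Section 9 list may be left over from a dose-escalation stage. That is plausible, but Sections 6.1 and 9 both stand as current text and neither describes stages. If stages exist, saying which doses belong to each is the reconciliation needed. The SAP does supply the missing injection size, so the regimen is defined in the document set. The protocol wording is still incomplete.

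The reply is stronger on Appendix 3, where a reader might infer three things that the documents do not support.

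- *That Appendix 3 restricts dosing to six levels.* It does not. It gives an interval, and 9.6 lies inside it. Only Section 9 lists levels.
- *That the two-injection arm exceeds the permitted dose.* This needs a cumulative reading. Sections 5.2 and 6.1 and the SAP all use the word dose for a single injection, which favours the per-injection reading. On that reading nothing is out of range. Appendix 3 also describes what will be given and does not call 12.8 a ceiling.
- *That the two-injection exposure escaped review.* Nothing shows this. Appendix 3 points to the Investigator's Brochure, Section 12 to a separate monitoring committee procedure, and Section 11.1 to the regulator's authorisation. None of these can be seen here.

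These replies leave Appendix 3 as a matter for clarification. They do not touch the conflict between Section 9 on one side and Section 6.1 and the SAP on the other, or the single-injection wording in the Study Summary and Appendix 1.

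**Conclusion.** The protocol and SAP give incompatible accounts of the regimen, and they cannot all be followed as written. None of the six Section 9 doses is 9.6 nmol/kg. Section 9 has no two-injection regimen, and its 90 women do not correspond to the SAP's 62. Two places in the protocol still describe one injection. This conclusion rests only on reading the current texts against each other.

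The consequences for the analysis are real. The sample size basis, the logistic dose model and the closure rule are all written for a design other than the one in the SAP.

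The Appendix 3 point is secondary and conditional. The range lacks a unit. The total of 19.2 nmol/kg would be 1.5 times its upper end if it is cumulative, while each injection is 0.75 of it if the range is per injection. The documents do not settle which applies, although their usage leans to per injection. No breach of a limit and no lapse in oversight is shown, and no view is taken on which dose or regimen is right.

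**What to change.** 1. Reconcile the Study Summary, Sections 6.1 and 9 and Appendices 1 and 3 of the protocol with the SAP, so that all state the same regimens, the number of injections and the size of each injection in both arms. If the study has stages, say which doses and how many women belong to each.
2. State in Appendix 3 whether the range is per injection or cumulative per woman, and confirm that the exposure reviewed by the monitoring committee and the regulator covers the two-injection arm.
3. Restate the Section 9 sample size basis and the primary analysis model, and the Section 8.2 closure rule, for the reconciled regimens. The recruitment figures should agree with this.

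The cost is amendment wording, one confirmation, and a rewritten sample size basis and primary analysis in Section 9. That last part is statistical work and not only editing. No new data collection is needed.
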